9.1.3 Study Procedures

9.1.3.1 Screening (up to 42 days before Day 0)

- Explain the nature of the study and have patients to read and sign an Informed Consent Form (ICF)
- Assign patient identifier (Screening number) to patients
- Obtain demographic characteristics
- Record medical and surgical history including cancer history
- Record medication history including cancer treatment history
- Screen patients for inclusion/exclusion criteria.
- Obtain a tissue sample (tumor biopsy or archived tumor tissue) to determine KRAS tumor mutation status prior to study enrollment. A patient may be enrolled based on KRAS test results from the local laboratory. Pleural fluid cytology may be used to determine KRAS mutation status if the cytology was pathologically reviewed and reported to contain malignant cells consistent with NSCLC. Tumor tissue from patients will also be used to evaluate arrays of genomic and proteomic markers of interest.
- Perform physical examinations. Weight, height and body mass index (BMI) will be measured at Screening Visit only
- Perform urine pregnancy test for applicable patients only. A urine pregnancy test will be performed during the Screening Visit for women of child-bearing potential. This test can be repeated during the study if required by local regulations
- Obtain vital signs. Vital signs (respiratory rate, heart rate, blood pressure, and body temperature) will be obtained in the sitting position after the patient has rested for 5 minutes. The date and time of the assessment should be recorded.
- Perform ECOG performance status evaluation (see [Appendix 2](#))
- Perform 12-Lead ECG examinations
- Perform clinical laboratory tests (hematology, biochemistry, and urinalysis)
- Tumor assessments (radiological and clinical tumor assessments). Evaluation at the Screening Visit must be performed within 14 (\pm 7) days of the date of first administration of study drug.

9.1.3.2 Visit 1 (Day 0)

- Record concomitant medications
- Perform physical examinations
- Obtain vital signs
- Perform ECOG performance status evaluation
- Perform 12-Lead ECG examinations

- Perform clinical laboratory tests (hematology, biochemistry, and urinalysis)
- Dispense study drug. All Screening procedures, laboratory results and repeat laboratory results must be available and reviewed before the patient receives the first dose of study drug
- Collect pre-dose blood sample within 30 minutes prior to dosing (Stage 1 only)
- Administer the first dose of study drug at site and collect PK blood samples 0.5, 1, 2, 3, 4, 6, and 8 hours after dosing (Stage 1 only)
- Document study drug dosing time
- Record AE and grade possible toxicity
- Calculate patient compliance
- Perform European Organization for Research and Treatment of Cancer (EORTC) Quality of Life Questionnaires (QLQ) (see [Appendix 3](#))

9.1.3.3 Visit 2 (Day 14 ± 3)

- Record concomitant medications
- Perform physical examinations
- Obtain vital signs
- Perform clinical laboratory tests (hematology, biochemistry, and urinalysis)
- Record AE and grade possible toxicity
- Calculate patient compliance

9.1.3.4 Visit 3 (Day 28 ± 3)

- Record concomitant medications
- Perform physical examinations
- Obtain vital signs
- Perform ECOG performance status evaluation
- Perform 12-Lead ECG examinations
- Perform clinical laboratory tests (hematology, biochemistry, and urinalysis)
- Dispense study drug
- Perform drug accountability
- Collect pre-dose blood sample 30 minutes prior to dosing (Stage 1 and 2; approximately 8 hours after the prior dose)
- Administer study drug at site and collect PK blood samples 0.5, 1, 2, 3, 4, 6, and 8 hours after dose (Stage 1 only). Stage 2 only: collect PK blood sample 3 hours after dose
- Document study drug dosing time

- Record AE and grade possible toxicity
- Calculate patient compliance

9.1.3.5 Visit 4 (Day 42 ± 3)

- Record concomitant medications
- Perform physical examinations
- Obtain vital signs
- Perform ECOG performance status evaluation
- Perform 12-Lead ECG examinations
- Perform clinical laboratory tests (hematology, biochemistry, and urinalysis)
- Tumor assessments (radiological and clinical tumor assessments)
- Perform drug accountability
- Collect pre-dose blood sample 30 minutes prior to dosing (Stage 2 only; approximately 8 hours after the prior dose)
- Administer study drug at site and collect random PK blood sample (Stage 2 only)
- Record AE and grade possible toxicity
- Calculate patient compliance
- Perform EORTC QLQ

9.1.3.6 Visit 5 (Day 56 ± 3)

- Record concomitant medications
- Perform physical examinations
- Obtain vital signs
- Perform ECOG performance status evaluation
- Perform 12-Lead ECG examinations
- Perform clinical laboratory tests (hematology, biochemistry, and urinalysis)
- Dispense study drug
- Perform drug accountability
- Collect pre-dose blood sample 30 minutes prior to dosing (Stage 2 only; approximately 8 hours after the prior dose)
- Administer study drug at site and collect random PK blood sample (Stage 2 only)
- Record AE and grade possible toxicity
- Calculate patient compliance

9.1.3.7 Visit 6 (Day 84 ± 3)

- Record concomitant medications
- Perform physical examinations
- Obtain vital signs
- Perform ECOG performance status evaluation
- Perform 12-Lead ECG examinations
- Perform clinical laboratory tests (hematology, biochemistry, and urinalysis)
- Tumor assessments (radiological and clinical tumor assessments)
- Dispense study drug
- Perform drug accountability
- Record AE and grade possible toxicity
- Calculate patient compliance
- Perform EORTC QLQ

9.1.3.8 End of Study (EOS) Visit (± 7 days)

Patients will attend an EOS Visit, 4 weeks after the last administration of study drug. In the event that a patient is scheduled to start a new treatment earlier than 3 weeks after the last dose of study drug, the EOS Visit should occur before the start of the new treatment and the reason documented.

- Record concomitant medications
- Perform physical examinations
- Obtain vital signs
- Perform ECOG performance status evaluation
- Perform 12-Lead ECG examinations
- Perform clinical laboratory tests (hematology, biochemistry, and urinalysis)
- Tumor assessments (radiological and clinical tumor assessments). Tumor assessment does not need to be performed at the EOS Visit if this was conducted at the Day 84 Visit. For patients participating in the Extension Phase, the tumor assessment does not need to be performed at the EOS Visit if it has been assessed within 8 weeks of the EOS Visit.
- Perform drug accountability
- Record AE and grade possible toxicity. Safety follow-up data may be collected by telephone contact every 3 months after the EOS Visit.
- Calculate patient compliance
- Perform EORTC QLQ

- All patients who withdraw from the study drug, but consent to be followed up for survival status, will be followed up by telephone contact every 3 months, for a maximum of 6 months from the date of last administration of study drug or death, whichever occurs first.

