
Name of Sponsor/Company: Golden Biotechnology Corporation	Individual Study Table Referring to Part of the Dossier: Volume: Page:	(For National Authority Use Only)
Name of Product: Hocena [®] 100 mg capsule		
Name of Active Ingredient: Antroquinonol		

 • Patients who have any other life-threatening illness or organ system dysfunction, which in the opinion of the investigator, would either compromise patient safety or interfere with the evaluation of the safety of the study drug • Known or suspected substance abuse or alcohol abuse • Women of child-bearing potential or men who are able to father a child unwilling to use two medically accepted and effective methods of contraception during the study (as specified in the inclusion criteria) • Pregnancy or breast feeding • Patient unable to comply with the protocol • History of clinically significant or uncontrolled cardiac disease, including congestive heart failure, angina, myocardial infarction, arrhythmia, including New York Heart Association functional classification of three 		

Test Product, Dose and Mode of Administration:
 
Antroquinonol 100 mg. Beginning on Day 0, patients will receive one 12-week cycle of antroquinonol 200 mg t.i.d. or until disease progression, unacceptable toxicity, non-compliance or withdrawal of consent by the patient, or the investigator decides to discontinue treatment, whichever comes first.
 
Study drug should be taken at 8-hour intervals with a glass of water, approximately 15 minutes after a meal or light snack, and not within ± 1 hour of drinking an ethanol-containing beverage, e.g. an alcoholic drink. The date and time of each study drug administration should be recorded in the patient diary.
 
After the first 12-week treatment cycle, patients who are progression-free will be eligible to receive further (12-week) treatment cycles with antroquinonol (Extension Phase), until documented evidence of disease progression, unacceptable toxicity, non-compliance or withdrawal of consent by the patient, or the investigator decides to discontinue treatment, whichever comes first. Investigators should wait at least 7 days after the last administration of study drug before initiating alternative treatment.
		

Reference Therapy, Dose and Duration of Administration:
 
Not applicable.
		

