Patients will attend study visits on Days 0, 14, 28, 42, 56 and 84 during the first 12-week treatment cycle, every 4 weeks during the second, third, and fourth treatment cycles (Extension Phase); and every 12 weeks during subsequent treatment cycles (Extension Phase). The study-specific procedures include: physical examination, vital signs, 12-lead ECG, performance status, clinical laboratory tests, AEs, concomitant medication and patient compliance. The schedule of assessments is presented in [Table 9.1](#).

Patients discontinuing study drug will attend an End of Study (EOS) Visit, 4 weeks after the last administration of study drug. In the event that a patient is scheduled to start a new treatment earlier than 3 weeks after the last dose of study drug, the EOS Visit should occur before the start of the new treatment and the reason documented.

Intensive PK sampling will be performed on Days 0 and 28 in all patients enrolled in Stage 1. Sparse PK sampling will be performed on Days 28, 42, and 56 in all patients enrolled in Stage 2.

All patients who withdraw from the study drug, but consent to be followed up for survival status, will be followed up by telephone contact every 3 months, for a maximum of 6 months from the date of last administration of study drug or death, whichever occurs first.

Tumor assessments will be performed at Screening, Days 42 and 84 using the Response Evaluation Criteria in Solid Tumors (RECIST) criteria, version 1.1 (see [Appendix 1](#)). Tumor assessments will be performed every 12 weeks during the Extension Phase.

The primary efficacy endpoint is progression-free survival (PFS) rate at 12 weeks, which is defined as the proportion of patients alive and progression-free at Week 12. Patients will be progression-free if they have no evidence of progressive disease (defined according to RECIST guidelines, version 1.1) from the start of treatment to Week 12.

The study uses a two-stage design seeking to detect a true PFS rate of more than 35% in the overall (unselected) population and 40% within the KRAS tumor mutation positive and negative strata. Thirty evaluable patients (15 in each stratum) will be treated initially (Stage 1), with expansion to a maximum of 60 evaluable patients (Stage 2). The rules for continuing the overall study and individual stratum are provided in [Section 14.2](#).

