It is important for the investigators to take information of underlying diseases, concomitant drugs, and temporal relationship of the onset of the event to the time of dosing the study drug, and re-challenging outcomes, into account when making a causal relation decision. It is the investigators' responsibility to follow proactively the outcome of each AE until resolution or stabilization of the condition, alternative treatment for NSCLC is started, 6 months after last dose of study drug, or loss to follow-up, whichever occurs first. In the event of serious or study drug-related toxicities, the patient will be followed until resolution or stabilization. Safety follow-up data may be collected by telephone contact every 3 months after the EOS Visit.

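### The End of Study Visit must precede new anti-cancer treatment only if that treatment starts before Day 21 after the last dose, yet the visit is due on Days 21-35, so starts on Days 21-34 can come before the EOS assessments

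*Protocol*

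**What the plan says.** Section 9.1.1 states: "Patients discontinuing study drug will attend an End of Study (EOS) Visit, 4 weeks after the last administration of study drug". Section 9.1.3.8 repeats the 4-week timing, and its heading and Table 9.1 add a window of ±7 days.

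The exception is given in the same terms in Section 9.1.1, Table 9.1 footnote 2 and Section 9.1.3.8. It begins "In the event that a patient is scheduled to start a new treatment earlier than 3 weeks after the last dose of study drug" and ends "the EOS Visit should occur before the start of the new treatment and the reason documented".

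The only stated minimum wait before other therapy is in the synopsis, Section 9.1.1 and Table 9.1 footnote 3: "Investigators should wait at least 7 days after the last administration of study drug before initiating alternative treatment".

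The EOS Visit comprises physical examination, vital signs, ECOG status, ECG, laboratory tests, adverse event recording, the EORTC questionnaires and a tumor assessment. The scan has two waivers. For the first cycle: "Tumor assessment does not need to be performed at the EOS Visit if this was conducted at the Day 84 Visit". In the Extension Phase it is waived if a scan was done within 8 weeks of the visit.

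Section 13.10.4 and Table 9.1 footnote 12 list several end points for adverse event follow-up, whichever comes first. One is that "alternative treatment for NSCLC is started". Serious or drug-related toxicities are excepted and followed to resolution or stabilization.

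**The concern.** The early-visit rule appears meant to complete the EOS assessments before the next therapy can influence them. It does this for starts before Day 21. From Day 21 onward it is silent, although the visit may still be up to two weeks away.

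Four uses of the data are exposed:

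- **Scan and FAS membership.** For a patient who stops before the study Day 42 scan, EOS is the only scheduled post-baseline tumor assessment. Section 14.2.1 admits an evaluable patient to the FAS on one post-baseline assessment, with no condition on new therapy. A scan under the next regimen could therefore bring the patient into the set used for the secondary analyses.
- **Week 12 status.** For some last-dose dates the EOS window overlaps the study Day 84 window, so a scan after new therapy could coincide with the primary time point.
- **Laboratory tests, ECG and questionnaires.** The protocol states no handling for values obtained after new therapy. The PRO population needs only the Day 0 questionnaire and one later one.
- **Adverse events.** Recording at an EOS Visit held after new therapy has begun fits poorly with the rule that follow-up ends when that therapy starts.

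**Working it through.** Days are counted from the last dose unless marked as study days.

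**Inputs.** Nominal visit: 4 weeks = Day 28 (Sections 9.1.1, 9.1.3.8). Window: ±7 days (Table 9.1, Section 9.1.3.8). Condition for an early visit: start before 3 weeks = before Day 21. Minimum wait before other therapy: 7 days. Study Day 84 visit: ±3 days.

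**Visit window.** 28 − 7 = 21 and 28 + 7 = 35, so Days 21-35.

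**Starts covered by the rule.** Days 7-20.

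**Starts not covered that can precede an in-window visit.** The start day s must satisfy s ≥ 21, with a visit day e such that s < e ≤ 35. This gives s = 21 to 34, which is 14 start days. A start on Day 35 could only share the day with the visit. With the visit held at Day 28, the condition is 21 ≤ s < 28, so s = 21 to 27, which is 7 start days.

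**Example.** Start on Day 22: a visit on Day 28 falls 28 − 22 = 6 days into the next regimen; a visit on Day 35 falls 35 − 22 = 13 days into it.

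**Could the site avoid this within the window?** Yes. For every s ≥ 21, Day 21 is an in-window visit day on or before s. For s = 21 the visit must come first on the same day.

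**Overlap with Week 12.** The study Day 84 window is study Days 81-87. An EOS Visit 21-35 days after the last dose can fall in it when the last dose is between study Day 81 − 35 = 46 and study Day 87 − 21 = 66. If the visit is at least one day after a Day 21 start, the upper limit is 87 − 22 = 65. So the range is about study Days 46-66.

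**Does another passage close the gap?** Section 10.10 bars other anti-cancer therapy during the study period. That period is not defined, and the ban stands beside the permission to start alternative treatment after 7 days. It cannot be read with confidence as running to the EOS Visit.

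**The case against.** The strongest reply is that the 3-week condition is coherent. It equals the opening day of the window. Before Day 21 no in-window visit can precede new therapy, so the protocol calls for an out-of-window visit with a documented reason. From Day 21 an in-window visit is available and needs no special permission. This is correct, and the rule is neither arbitrary nor self-contradictory. But an available visit is not a required one, and a site that books the nominal Day 28 complies with the text.

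A reader might infer that scans under the next regimen bias PFS and TTP. The documents do not support that. Section 14.2.2.2 leaves the censoring rules to the SAP, which is not shown. A patient withdrawn for documented RECIST progression already has a progression date that a later scan would not normally move. Best overall response is protected, because Appendix 1 excludes post-treatment assessments and censors patients given other therapy. Under Section 14.2.2.1, patients who discontinue without a post-screening or Week 12 assessment count as failures. What remains is that a censoring rule can discard an affected scan but cannot supply the clean one that was not taken.

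A reader might also infer that the next regimen's toxicity will be attributed to antroquinonol. That does not follow either. Section 13.10.4 has causality judged event by event, taking account of other therapy and timing, and concomitant medication is recorded at the EOS Visit. The exception for serious or drug-related toxicities, and the 30-day SAE reporting duty in Section 13.10.5, both support safety collection after new therapy starts. The follow-up rule therefore does not plainly forbid EOS adverse event recording; the two passages are just not aligned.

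**Conclusion.** The gap is real and appears in all three statements of the rule. Starts on Days 21-34 are exposed across the full window, or Days 21-27 at the nominal visit date. The consequence is limited. The scan is at issue only where one is due: no study Day 84 scan in the first cycle, or none within 8 weeks in the Extension Phase. In those cases it may be the only scheduled post-baseline scan supporting FAS entry or, for a last dose on about study Days 46-66, may coincide with Week 12. EOS laboratory, ECG and questionnaire data may likewise reflect the next regimen.

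No bias in PFS, TTP or the safety summaries can be asserted. The documents do not say how many patients restart therapy in this interval, so the number affected is unknown. The conclusion assumes that the study period in Section 10.10 is not meant to extend to the EOS Visit; if it is, the protocol should say so. The correction is worth making because it is cheap and the clean assessment cannot be recovered later.

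**What to change.** In Section 9.1.1, Table 9.1 footnote 2 and Section 9.1.3.8, replace the 3-week condition with *before the EOS Visit has taken place*, so that all EOS assessments precede any new anti-cancer treatment. Keep the requirement to document the reason when the visit falls before Day 21. Reconcile adverse event recording at the EOS Visit with the end-of-follow-up rule in Section 13.10.4 and Table 9.1 footnote 12.

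This adds no visit or procedure. For any start on Day 21 or later the visit still fits the existing window. The change governs the order of assessments only and does not set when any treatment may begin. The cost is a somewhat earlier EOS Visit for affected patients: at most 28 − 21 = 7 days before the nominal date for starts from Day 21 onward.

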9.1.3.9 Extension Phase Visits (± 7 days)

Patients will attend visits every 4 weeks (± 7 days) during the second, third, and fourth treatment cycles. After completion of the fourth treatment cycle, patients will attend visits every 12 weeks (± 7 days).

- Record concomitant medications
- Perform physical examinations
- Obtain vital signs
- Perform ECOG performance status evaluation
- Perform 12-Lead ECG examinations
- Perform clinical laboratory tests (hematology, biochemistry, and urinalysis)
- Tumor assessments (radiological and clinical tumor assessments)
- Dispense study drug
- Perform drug accountability
- Record AE and grade possible toxicity
- Calculate patient compliance
- Perform EORTC QLQ

9.2 Discussion of Study Design

9.2.1 Rationale for Single-Arm, Open-Label Phase II Study

This is a single-arm, open-label, Phase II study in KRAS-positive and KRAS-negative patients with stage IV (including pleural effusion) non-squamous NSCLC who have failed two lines of anti-cancer therapy. This is defined as patients with radiologically confirmed disease progression following greater than or equal to two, but less than or equal to four, prior lines of systemic anti-cancer therapy (see [Section 9.3.1](#) for a detailed description of the eligibility criteria). The rationale for this study is outlined in [Section 7.5](#) and described in more detail below.

The subject population of patients with stage IV (including pleural effusion) non-squamous NSCLC who have failed two lines of anti-cancer therapy was chosen for this study as there is a current unmet need to treat this population and results from the first-in-man Phase 1 study indicate that the tumor overall response at the end of treatment showed stable disease for all three patients (one patient in the 200 mg dose group and two patients in the 600 mg dose group) included in the per-protocol set (PPS). The PPS was defined in the Phase 1 study as all patients who completed at least three cycles of treatment with proper imaging assessment

(RECIST v.1.1). Furthermore, antroquinonol at 50, 100, 200, 300, 450, and 600 mg dose levels, given daily for 4 weeks, was generally safe and well tolerated, with no particular safety concerns or DLT being identified in the study.

Preclinical data (see [Section 7.3](#)) suggest that patients with KRAS mutation positive tumors may derive greater benefit from antroquinonol therapy. Hence, patients will be stratified according to KRAS mutation status.

An open-label design was selected as this was considered the most suitable design for evaluation of antroquinonol as a single agent in the patient population eligible for participation in this study.

A two-stage, single-arm design was chosen as this was considered most suitable for assessing the safety, tolerability, PK and efficacy of antroquinonol in patients who have previously failed two lines of anti-cancer therapy.

Antroquinonol will be administered as a single agent in this study at a dose of 600 mg per day (200 mg t.i.d. administered at 8-hour intervals). This dose regimen was chosen based on results from the Phase 1 clinical study (GOLANTA20090911) involving NSCLC patients refractory to conventional treatment modalities, which reported good tolerability of antroquinonol up to 600 mg/day. The area under the plasma concentration-time curve from 0 to 24 hours (AUC_{0-24}) after single dose administration on Day 1 of the first treatment cycle (Cycle 1) increased by 18.79%, 200.1%, 215.16%, 265.19% and 396.61% at the 100, 200, 300, 450, and 600 mg dose levels, respectively, when compared with the 50 mg dose level; whereas on Day 28 of Cycle 1, the AUC_{0-24} decreased by 34.88% at the 100 mg dose level and increased by 133.58%, 141.87%, 680.65% and 562.54% at the 200, 300, 450, and 600 mg dose levels, respectively. Thus, the AUC_{0-24} was not linearly proportional to the antroquinonol dose on Day 1 and Day 28. There were no significant differences in AUC_{0-24} in the 100-300 mg dose range on Day 1 and Day 28. The highest peak concentration (C_{max}) over the 100-300 mg dose range was observed with the 200 mg dose on Day 28. One patient in the 200 mg dose group and two patients in the 600 mg dose group exhibited stable disease at the end of treatment.

Thus, in order to maintain a high drug concentration and enhance the efficacy of antroquinonol 200 mg t.i.d. (every eight hours) has been chosen as the dosage regimen for this study.

The study design is based on the assumption that within each of the KRAS tumor mutation positive and negative strata, a PFS rate at 12 weeks of 40% and 35% overall would be of interest. Further testing would not be pursued if the PFS rate at 12 weeks was less than 15%. See [Section 14.1](#) for further details.

The study drug will be administered until disease progression, occurrence of unacceptable toxicity, non-compliance or withdrawal of consent by the patient, or investigator decision to stop study drug, whichever comes first.

